4.0	DESCRIPTION OF THE INVESTIGATIONAL DEVICE	22
5.0	MONITORING PROCEDURES	22
6.0	LABELING	22
7.0	INFORMED CONSENT.....	22
8.0	IRB INFORMATION	23
9.0	ADDITIONAL RECORDS AND REPORTS	23
9.1	Data handling and record-keeping	23
9.2	Record maintenance and retention	23

LIST OF ABBREVIATIONS

AE	Adverse Event
CFR	Code of Federal Regulations
CRF	Case Report Form
DMC	Data Monitoring Committee
DSMB	Data Safety Monitoring Board
FDA	Food and Drug Administration
GCP	Good Clinical Practice
HIPAA	Health Insurance Portability and Accountability Act of 1996
ICF	Informed Consent Form
ICH	International Conference on Harmonisation
IEC	Independent Ethics Committee
IRB	Institutional Review Board
QC	Quality Control
PI	Principal Investigator
UADE	Unanticipated Adverse Device Effect

PROTOCOL SYNOPSIS

TITLE	A Pilot Study to Evaluate a Temporary Skin Substitute (Spincare™ Matrix) for Wound Healing in RDEB patients
REGULATORY SPONSOR	[name], PhD
FUNDING ORGANIZATION	EB Research Partnership
NUMBER OF SITES RATIONALE	
Single site
 
Of the various EB subtypes, it is well known that recessive dystrophic epidermolysis bullosa (RDEB) patients suffer from the most severe skin wounds. In this pilot study we will enroll RDEB patients due to their need for specialized wound care, which is typically more complex and frequent than other types of EB. Therapies that reduce pain and the size and severity of wounds have also been reported as the main priorities for RDEB patients and caregivers. There are limited therapies approved in the US for the treatment of EB and there has been an exponential rise in EB-related studies. The mainstay of treatment is supportive with non-adhesive wound dressings.
 
With the lack of therapies available to address the multitude of RDEB needs and the slow pace of EB research, we propose to evaluate the matrix device as a suitable and safe device for application of a matrix wound dressing to EB wounds. This study is looking at preliminary wound efficacy signals and tolerability.
 
Results of this pilot study would inform the design of larger trials evaluating the suitability of the device as a vehicle in delivering COL7A1 gene-corrected skin cells for healing of RDEB wounds. This is currently under research development by [name] Lab at Stanford.

STUDY DESIGN	This is a single-center, randomized feasibility study that offers an Open-Label Phase upon completion of the Randomized Phase.
PRIMARY OBJECTIVE	
To assess the preliminary efficacy of matrix treatment in RDEB wound
 
To assess safety profile of matrix treatment in RDEB wound

SECONDARY OBJECTIVES	To assess improvement in wound pain with matrix treatment in RDEB wound To assess improvement in wound itch with matrix treatment in RDEB wound To assess caregiver responses on wound dressing ease of use with matrix treated wounds To compare the change in wound cultures between matrix treated wounds vs control wounds
NUMBER OF SUBJECTS	6-10 subjects for enrollment of at least 20 wound pairs
SUBJECT SELECTION CRITERIA	
Inclusion Criteria: Clinical and/or genetic diagnosis of RDEB by a dermatologist, age 6 years or older willing and able to give consent/assent and have at least 6 wounds (3 wound pairs) each with an area of 10cm² or greater located at any site (excluding face and genital skin). The first patient that will be enrolled is an adult patient before the recruitment of pediatric patients. Wounds must be present for at least 4 weeks and able to be classified as recurrent wounds (wounds that heal within 12 weeks but then re-blister) vs chronic open (older than 12 weeks).
 
Exclusion Criteria: Actively infected wounds with pus (colonized wounds are eligible), areas that have had squamous cell carcinoma (SCC), areas on the face and genitals, and areas that have been treated with investigational therapies in the past 3 months.

INVESTIGATIONAL DEVICE / INTENDED USE	Spincare The Spincare matrix is delivered from a portable, hand-held device that produces an electrospun healing matrix made of biocompatible materials that attaches directly to the wound bed.
CONTROL GROUP OR OTHER STUDY ARMS (if applicable)	Standard of care non-adhesive wound dressings and bandage changes currently used.
DURATION OF SUBJECT PARTICIPATION AND DURATION OF STUDY	Subjects will be on study for up to 4 months Screening: performed over phone and then virtually (up to 30 days before Day 0 treatment day) Treatment: 1-3 days (subjects to attend clinic) Follow-up: 4 months Open-Label Phase: 4 months The total duration of the study is expected to be 1 year. 4 months for subject recruitment and 6 months for final subject follow-up is anticipated.

CONCOMMITANT MEDICATIONS	Allowed: current EB medications (i.e., pain meds, vitamins, iron infusions, antibiotic ointments, oral antibiotics if needed). Prohibited: none
Efficacy Evaluations	Greater than 90% wound closure, patient reported outcomes in pain and itch sensation
Primary endpoint	Comparison of the duration of wound closure (weeks) of matrix treated wounds vs control wounds from baseline to Month 4. Wound photos will be captured at least every 2 weeks by the patient and/or caregivers. The matrix will be applied initially in clinic and afterwards patients/caregivers are allowed to apply the Spincare treatment (up to once a week) to the designated treatment wounds if required. They will receive adequate training at the in-person and/or remotely visits before applying it.
Secondary endpoints	
 1. Comparison of application site adverse events (burning, erythema, pain) between matrix treated wounds vs control wounds after application. 2. Comparison of wound pain (Wong-Baker FACES scale) between matrix treated wounds vs control wounds at Month 1, Month 2, Month 3, Month 4 (prior to application). More frequent timepoints may be requested. 3. Comparison of wound itch [Itch Severity Scale (adults) / Itchy Man scale (minors)] between matrix treated wounds vs control wounds at Month 1, Month 2, Month 3, Month 4 (prior to application). More frequent timepoints may be requested. 4. Comparison of wounds that reach >50% healing from baseline in matrix vs control wounds at month 1, 2, 3, 4. 5. Comparison of wounds that reach >70% healing from baseline in matrix vs control wounds at month 1, 2, 3, 4.
Other Evaluations	
 1. Comparison of caregiver responses on wound dressing ease of use on matrix treated wounds vs control wounds with the Caregiver Global Impression of Change survey (CaGI-C) at Month 3 and Month 4.

	2. Comparison of change in wound cultures between matrix treated wounds vs control wounds at Month 2 and Month 4.
Safety Evaluations	Wound evaluation e.g. presence of infection or skin cancer and documentation of adverse events.
Planned Interim Analyses	None. 1 adult subject to be enrolled first to ensure tolerability and safety before treating pediatric EB subjects > 6 years of age.
STATISTICS Primary Analysis Plan	
Sample size calculation: We calculated that a sample size of 40 wounds (20 matrix-treated vs 20 untreated) would give us 90% power to detect a difference of 8.5 vs 6 weeks (SD=3) of wound closure duration between matrix treated vs untreated wounds with a two-sided alpha of 0.05.
 
Recruitment plan: We will recruit our cohort of 6-10 patients from various settings including the Stanford EB clinic (~100 RDEB patients), our clinical research database (75 RDEB patients), and the Epidermolysis Bullosa Clinical Research Consortium (EBCRC) (290 RDEB patients). Many of these patients have already received a clinical and/or genetic diagnosis of RDEB and have detailed medical and wound histories recorded

Rationale for Number of Subjects	This sample size calculation is based on our prior natural history study of 720 RDEB wounds for 6 months in 13 RDEB adult and pediatric participants. We anticipate that the majority of pediatric wounds will be the recurrent type. If the Spincare matrix decreases the duration of wound closure, then this clinical trial would show a novel wound healing device that may improve wound closure duration in difficult to heal RDEB wounds. We would assess the secondary endpoints to determine if a 2.5 week longer wound closure is clinically meaningful and associated with wound specific decreases in pain and itch.

1.0 PURPOSE OF THE INVESTIGATION

1.1 Name of investigational device

Spincare matrix

1.2 Intended use of the investigational device

The Spincare device, developed by Nanomedic, is the first portable tool that delivers an electrospun, nanofibrous matrix dressing to wounds to promote healing that is approved in Europe. The aim of this pilot study is to determine the suitability of this device in RDEB wounds and assess its wound healing properties, safety and tolerability, particularly in the EB population.

1.3 Objectives of the clinical investigation

1.3.1 Primary objective

1. Evaluate the efficacy and safety of the device on wounds in patients with recessive dystrophic epidermolysis bullosa.

1.3.2 Secondary objective(s)

2. To evaluate the improvement in patient reported pain and itch sensation with the matrix treatment.
3. To evaluate patient and caregiver responses on wound dressing ease of use on matrix treated wounds vs control wounds with the Caregiver Global Impression of Change survey (CrGI).
4. To compare the change in wound cultures between matrix treated wounds vs control wounds at Month 2 and Month 4.

1.4 Anticipated duration of the clinical investigation: 10 months

2.0 CLINICAL PROTOCOL

2.1 Protocol number and title

IRB-69575: A Pilot Study to Evaluate a Temporary Skin Substitute (Spincare™ Matrix) for Wound Healing in RDEB patients

2.2 Protocol version number and date

Version 4.0, 05 June 2024

2.3 Study design

[figure not shown]
2.3.1 General study design

Pilot study in 6-10 subjects where wounds will be randomized 1:1 to matrix or no treatment (control): Patients will be asked to review and sign the informed consent form. The matrix will be applied to randomized treatment wounds (computer generated randomization), along with a non-adhesive bandage as a protective layer. At the time of matrix application, the investigator will score amount of wound burning, pain, or other adverse events. Non-treated wounds will have the patient's standard of care, and the non-adhesive bandage applied. Reapplication of matrix treatment may be required soon after the initial application depending on how well the matrix has propagated with the first application. Subjects and caregivers will be trained on how to take photos. We will ensure that photos of the face are NOT included to protect patients' confidentiality. One day after a wound examination will be performed in clinic. The investigator will assess the adherence of the matrix, and any adverse events (AEs).

Thereafter a caregiver may travel to the participants home to apply the matrix device to randomized, treated wounds once a month or more frequently if required (up to once-a-week application is allowed, the patient will record when they have applied the matrix treatment at home and the reason). Spray application(s) may be skipped at the discretion of the PI to address any concerns or adverse events. Investigators will perform remote monitoring (via phone call or virtual platform) at Week 1, Week 2, Month 1, Month 2, Month 3 and Month 4 (additional interim visits may be required) to assess for adverse events and track progress. Additional photographs will be taken, and investigators will use Telehealth to monitor for healing and safety reporting. Compliance is verified by bi-weekly photographs. Wound swabs of treated and untreated wounds will be taken prior to spray treatment and at Month 2 and Month 4. After Month 1, patients are given the option to not put any dressings on their wounds if this is medically acceptable and in line with the patient preference. Throughout the visit wound closure assessments may not be always possible if the Spincare matrix is still intact and this will be indicated on the source document. No Spincare treatment is to be applied 2 weeks prior to the end of the visit to allow for wound size measurement.

After the completion of the 4-month randomized phase, patients will be allowed to choose to enroll in an Open-Label Phase for an additional 4 months. Investigators will conduct remote monitoring on a monthly basis to assess adverse events and wound healing.

2.3.2 Study design schematic

2.4 Subject selection

2.4.1 General characteristics of the proposed subject population(s)

Patients aged 6-65 years old with a clinical and/or genetic diagnosis of recessive dystrophic epidermolysis bullosa. This target population was chosen as they suffer from large painful wounds usually resistant to conventional treatment and would benefit the most from matrix treatment with the Spincare device.

2.4.2 Anticipated number of research subjects

6-10 patients are planned to be recruited in the study.

2.4.3 Inclusion criteria

1. Subject has a clinical and/or genetic diagnosis of RDEB by a dermatologist;
2. Subject is age 6 years or older willing and able to give consent/assent;
3. Subject has at least 6 wounds (3 wound pairs) each with an area of 10cm² or greater located at any site (excluding face and genital skin);
4. Subject wounds must be present for at least 4 weeks.

2.4.4 Exclusion criteria

1. Actively infected wounds with pus (colonized wounds are eligible);
2. Wound areas that have had squamous cell carcinoma (SCC);
3. Wound areas on the face and genitals;
4. Wound areas that have been treated with investigational therapies in the past 3 months.

2.5 Study procedures**2.5.1 Screening procedures**

Patients will be screened based on the inclusion and exclusion criteria. This will be initially performed over the phone. If eligible a virtual meeting will be organized, and patients will be asked to review and sign the informed consent form after which the wounds would be assessed in terms of suitability.

2.5.2 Study treatment or diagnostic product procedures

The Spincare device produces a wound dressing matrix that is sprayed to the wound bed. It uses a laser system to help with correct distance position to produce a uniform matrix that is electrospun to the wound bed. The device is currently available in Israel and 11 European countries but is not FDA-approved or cleared on any indications. In the current literature the main indications are acute and chronic wounds, partial thickness burns and ulcers and the matrix treatment has been used in more than 20 countries so far. A case study of Spincare treatment in EB has been described.

A full body wound examination will be performed by the investigator and target wound areas will be identified. All eligible wound sites will be randomized for matrix treatment versus standard of care wound dressings (6 wounds, or 3 wound pairs). The matrix will be applied to randomized treatment wounds, along with a non-adhesive bandage (e.g. Telfa, Mepitel, Rylon, etc.) as a protective layer. At the time of matrix application, the investigator will ask about any potential wound burning sensations, pain, or other adverse events. Non-treated wounds will have the patient's standard of care and non-adhesive bandage applied. Subjects and caregivers will be trained on how to take photos. Wound pain and itch are captured at least every 2 weeks.

The matrix treatment will be applied on Day 0 in clinic. Day 1 visit will be mandatory to assess for any adverse events (Day 2 is optional and may be required particularly if AEs have occurred and this will be at the discretion of the

PI). Subsequent applications will be performed by a caregiver if needed up to once a week.

Detailed Schedule:

Randomized phase:

Day 0 – Spincare would be applied to wounds after randomization process and covered with a non-adhesive dressing. Reapplication of matrix treatment may be required depending on how well the matrix has adhered with the first application. The need for this will be assessed by the investigators.

Day 1 – A wound examination will be performed in clinic one day after the initial application. The investigator will assess the adherence of the matrix, and any adverse events (AEs).

Day 2 is optional and may be required if medically indicated at the discretion of the PI.

Week 1, Week 2, and Months 1, 2, 3, 4 – Investigators will arrange telehealth assessment at Week 1, Week 2, Month 1, Month 2, Month 3 and Month 4 (additional interim phone call visits/telehealth assessment at **Week 6, Week 10 and Week 14**, or more frequently, if deemed necessary). A caregiver may travel to the participants home to apply the matrix device to randomized, treated wounds (up to once a week if needed, they will record the date of application and the reason). Additional photographs will be taken, and investigators will use Telehealth to monitor for healing and safety reporting. At the time of matrix application, the caregiver will score amount of wound burning, pain, or other adverse events. Matrix will not be applied after **Week 14** to ensure the final wound assessment at Month 4.

Month 4 – Telehealth (End of Randomized Phase) Visit: The investigator will virtually assess wound healing compared to baseline photographs in the treated and control wounds. Digital photographs of the treatment and control wounds will be taken with a ruler by the caregiver/participant and sent to the investigator. All wound photos will be stored and reviewed on the REDCap. The participant's preference to enroll on the Open-Label Phase will be assessed.

Open-Label Phase:

Participants who are eligible for the Open-Label Phase, at the discretion of the investigators (taking into consideration participant's prior documented adverse events, current medical status, and adherence to trial protocol), and who choose to participate, will be provided with the Spincare matrix and will be instructed to apply it once a week at most. Participant will be allowed to treat previously randomized wounds (treated and control wounds) and new wounds, up to a max of 10 individual wounds; there won't be control nor randomized wounds. The wounds would be selected at the Open-Label Baseline remote visit and will need to meet the same wound criteria as the Randomized phase. At minimum during each monthly visit, participants will be required to provide digital photos taken with a ruler before and after the application of the Spincare matrix. Additionally, they will complete surveys regarding their pain and itch, offer updates on their

medical history, provide information about concurrent medications, and report any adverse events. No blood draws, wound cultures and in person visits will be required during the Open-Label phase.

This extension phase will be 4 months long and will take place after the participants complete the Randomized phase.

Participants who elect to participate in the Open-Label Phase will undergo remote visits at **Open-Label Baseline** (could be done during the Month 4 of the Randomized Phase), **Open-Label Month 1**, **Open-Label Month 2**, **Open-Label Month 3**, and **Open-Label Month 4**.

Open-Label Baseline visit – Telehealth visit. Participant will have up to two weeks after the end of the Randomized Phase to enroll in the Open-Label Phase. At the Open-Label Baseline visit the Investigator will select up to 10 wounds from previously randomized (treated and control) wounds and new wounds (that meet the initial wound criteria). Medical history, con-medications, and adverse events will be reviewed. Spincare matrix will be applied on the new wounds, digital photographs of the wounds from before and after will be taken with a ruler by the caregiver/participant and sent to the research team. Participant will complete baseline pain and itch surveys.

Open-Label Months 1, 2, 3, 4 – Investigators will arrange telehealth assessment visits at Open-Label Month 1, Open-Label Month 2, Open-Label Month 3 and Open-Label Month 4 (additional interim remote assessments if deemed necessary). A caregiver may travel to the participant's home to apply the matrix device to the treated wounds (up to once a week if needed, they will record the date of application and the reason). Photographs will be taken, and investigators will use Telehealth to monitor for wound healing and safety reporting. At the time of matrix application, the caregiver will notate any wound burning sensations, pain, or other adverse events. Matrix will not be applied after **Open-Label Week 14** to ensure the final wound assessment at Open-Label Month 4.

Open-Label Month 4 – Telehealth (End of Open-Label Phase) visit. The investigator will virtually assess wound healing compared to baseline photographs in the treated wounds. Photos of the treated wounds will be collected by the caregiver/participant and sent to the research team. All wound photos will be stored and reviewed on the REDCap.

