2.6 Study outcome evaluations

2.6.1 Study endpoints

Primary endpoint:

Comparison of the duration of wound closure (weeks) of matrix treated wounds vs control wounds from baseline to Month 4. Wound photos will be captured bi-weekly by caregivers.

Secondary endpoints:

1. Comparison of application site adverse events (burning, erythema, pain) between matrix treated wounds vs control wounds after application;
2. Comparison of wound pain (Wong-Baker FACES scale) between matrix treated wounds vs control wounds at month 1, month 2, month 3, month 4 (prior to matrix application);
3. Comparison of wound itch (Itch NRS/Itchy Man scale) between matrix treated wounds vs control wounds at month 1, month 2, month 3, month 4 (prior to matrix application);
4. Comparison of wounds that reach >50% healing from baseline in matrix vs control wounds at month 1, 2, 3, 4;
5. Comparison of wounds that reach >70% healing from baseline in matrix vs control wounds at month 1, 2, 3, 4.

Exploratory endpoints:

1. Comparison of caregiver responses on wound dressing ease of use on matrix treated wounds vs control wounds with the Caregiver Global Impression of Change (CrGI);
2. Comparison of change in wound cultures between matrix treated wounds vs control wounds at Month 2 and Month 4,

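### Secondary endpoint 1 compares application-site events between arms, but scoring is triggered only by matrix application, so treated wounds can be asked about more often than controls and no same-session control answer is specified

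*Combined protocol and SAP*

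**What the plan says.** Section 2.6.1 and the synopsis list secondary endpoint 1 as "Comparison of application site adverse events (burning, erythema, pain) between matrix treated wounds vs control wounds after application". Neither gives an assessor, a time window, a source record or a reference time for control wounds, which receive no application.

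Scoring at application is described three times, each time triggered by the matrix:

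- Section 2.3.1, in clinic: "At the time of matrix application, the investigator will score amount of wound burning, pain, or other adverse events".
- Section 2.5.2, in clinic: "At the time of matrix application, the investigator will ask about any potential wound burning sensations, pain, or other adverse events".
- Section 2.5.2, Detailed Schedule, at home: "At the time of matrix application, the caregiver will score amount of wound burning, pain, or other adverse events".

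For control wounds, Sections 2.3.1 and 2.5.2 mention standard of care and a bandage. They neither require nor exclude a matching score. Erythema belongs to the endpoint but is not named in any of the three instructions.

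Other collection covers both arms:

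- Section 2.5.2 states "Day 1 visit will be mandatory to assess for any adverse events", and "Wound pain and itch are captured at least every 2 weeks".
- Section 2.5.8 has investigators assess erythema.
- Section 3.2.2 has subjects questioned about AEs at every visit.
- Section 3.2.3 sends all adverse effects to the case report form, and Section 9.1 names the paper form and REDCap.

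Section 2.5.5 places home applications at Weeks 1 and 2 and Months 1 to 3 if needed, and allows up to one a week. Section 2.5.2 allows none after Week 14. The schedule in Section 2.5.9 marks home application at Weeks 6 and 10 but leaves the adverse-event row blank at Weeks 6, 10 and 14.

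**The concern.** Safety is part of the primary objective (synopsis and Section 1.3.1), and endpoint 1 is the only listed endpoint that compares AEs between arms. If application-time scores feed it, matrix wounds are asked about on extra days whenever matrix is applied away from a contact that elicits AEs. More asking produces more recorded events without any device effect.

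There is also a question of interpretation. Section 3.1 names burning, pain and itch on application as an anticipated risk. Wounds in this disease hurt anyway, and so does handling them. A score taken on the treated wound alone cannot separate irritation by the device from background or handling pain. An answer about the control wound in that same session cannot be collected afterwards.

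Finally, each patient carries both treated and control wounds, while Sections 3.2.2 and 3.2.3 question and record by subject. Unless the wound is recorded, a burning or erythema entry on the case report form may not be assignable to an arm.

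**Working it through.** The plan gives no figure for this endpoint, so there is none to reproduce. The check counts the distinct days on which a wound is asked about or scored in the randomized phase, taking Month 4 as Week 16 (Section 2.5.7).

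**Control wounds**

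- *Reading A: every contact elicits AEs* (Section 3.2.2 taken literally, including the "additional interim phone call visits/telehealth assessment at" Weeks 6, 10 and 14). Day 0, Day 1, Weeks 1, 2, 4, 6, 8, 10, 12, 14 and 16 make 11.
- *Reading B: only contacts marked in the adverse-event row of Section 2.5.9, plus Day 0*, which the timeline under the table lists for AE monitoring. Day 0, Day 1, Weeks 1, 2, 4, 8, 12 and 16 make 8.

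**Matrix wounds** have the control set plus any application day outside it. Weekly use is Day 0 and Weeks 1 to 14. Under A it adds Weeks 3, 5, 7, 9, 11 and 13: 11 + 6 = 17. Under B it also adds Weeks 6, 10 and 14: 8 + 9 = 17.

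With the same event rate per occasion in both arms and no recall between contacts, the expected event-count ratio is matrix occasions divided by control occasions.

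| Reading | Applications | Matrix | Control | Ratio |
|---|---|---|---|---|
| A | Section 2.5.5 visits only, or two-weekly | 11 | 11 | 1.00 |
| A | Weekly | 17 | 11 | 1.55 |
| B | Section 2.5.5 visits only | 8 | 8 | 1.00 |
| B | As marked in Section 2.5.9 (adds Weeks 6, 10) | 10 | 8 | 1.25 |
| B | Two-weekly (adds Weeks 6, 10, 14) | 11 | 8 | 1.38 |
| B | Weekly | 17 | 8 | 2.13 |

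**Recall.** Suppose a fraction *f* of control events on the missed days is reported at the next contact. Under weekly use the ratio becomes:

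- A: 17/(11 + 6*f*), which is 1.55, 1.21, 1.08 and 1.00 at *f* = 0, 0.5, 0.8 and 1.
- B: 17/(8 + 9*f*), which is 2.13, 1.36, 1.12 and 1.00.

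**Wounds with at least one event.** If wounds rather than events are counted, the chance is 1 − (1 − *p*)^*k* over *k* independent occasions. At an assumed *p* = 5% with no recall, this is 58% for *k* = 17, 43% for *k* = 11 and 34% for *k* = 8. In 20 wounds, 17 against 11 occasions gives 11.6 against 8.6 wounds. Under a beta-binomial model with an assumed within-wound correlation of 0.1, 17 against 11 gives 40% against 32%. At a correlation of 0.3 it gives 24% against 21%, or 4.8 against 4.1 wounds. With independence, *p* = 2% gives 29% against 20%, and *p* = 10% gives 83% against 69%. All these rates and correlations are assumptions.

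**Common contacts.** Day 1, Weeks 1 and 2, and Months 1 to 4 give 7 occasions in each arm, a ratio of 1.00.

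**The case against.** The strongest reply is that the plan already collects AEs in both arms and that the imbalance is hypothetical. Much of this stands.

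A reader might infer that no source record exists, or that control wounds are never asked about. The documents do not support either. Sections 3.2.3 and 9.1 name the case report form and REDCap, Section 3.2.2 covers every visit, and Section 2.5.8 is not limited to treated wounds. What is missing is a link from any of these to endpoint 1, and attribution of each event to a wound.

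A reader might also take 1.5 or 2.1 as the expected bias. Those are ceilings. Weekly use is a maximum, allowed if needed. No section says that application-time scores enter endpoint 1. Subjects questioned at a visit may well report what happened since the last one. Scoring is also unblinded (Section 2.5.4), which could move results in either direction.

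The loss of information is partial. Background pain in control wounds is captured at least every two weeks, and secondary endpoint 2 compares wound pain between arms. That comparison is made before application, however. It gives neither burning nor same-session handling pain.

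The Day 1 visit offers a shared time point: "A wound examination will be performed in clinic one day after the initial application". It follows only the first application, and later home applications have no equivalent.

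Finally, a comparison at common visits alone would not serve the endpoint fully. Monthly contacts may fall weeks after the last application, and Month 4 comes after the Week 14 cut-off. They can miss brief application reactions, so a paired score at application is needed as well.

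**Conclusion.** The point holds in a limited form. Followed as written, the plan can give treated wounds more eliciting occasions than controls and provides no same-session control answer. It leaves open which record feeds endpoint 1 and to which wound an event belongs.

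The imbalance in occasions is at most 17 against 11, or 17 against 8, depending on whether Weeks 6, 10 and 14 elicit AEs. The corresponding event-count ratio with no true difference is at most about 1.5 to 2.1. That requires weekly use, application-time scores entering the endpoint, and no recall of control events. It falls to 1.0 with full recall, or when matrix is applied only at contacts that elicit AEs.

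The documents do not show that the comparison will be biased against the device, only that it is not protected from this. For a secondary safety endpoint in a pilot, the change should be made because it is cheap and the paired answer cannot be recovered later.

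**What to change.** 1. Whenever a treated wound is scored at application, including Day 0, ask the same burning and pain questions about its matched control wound in the same session. Make this within-pair comparison the application-time part of endpoint 1. The wounds are already matched under Section 2.5.3.
2. Record the wound for each application-site AE. Compare visit-elicited AEs, including investigator-assessed erythema, only at the contacts common to both arms: Day 1, Weeks 1 and 2, and Months 1 to 4. Keep these records separate from any application-time score on the same day, and state that they may miss transient application reactions.
3. Report application-time scores that lack a paired control score descriptively, for matrix wounds only.

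The cost is a wound identifier on the AE record and a few added form items per session. No visit, staff or dressing removal is added, and no treatment rule changes.
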